### **27 Missing data**

Missing data will not be imputed.

### **28 Harms**

These will be presented in Table describing serious adverse events.

**29 Statistical software**

Statistical Analysis System (SAS) version 9.4 (or later), SAS Institute Incorporation, Cary, North Carolina.

**SECTION 7. ADDITIONAL INFORMATION****30 Governance**

The trial is funded by the Nottingham University Hospitals NHS Trust Charity and sponsored by the University of Nottingham. The trial is managed by a Trial Management Committee (TMC), supervised by a Trial Steering Committee (TSC) and overseen by an independent Data Monitoring Committee (DMC).

**31 Minimising bias**

Multiple approaches will be taken to minimise bias: central data registration with real-time on-line validation; minimisation at randomisation; stratification by stroke type (IS or not known; ICH); inclusion of patients enrolled in other studies (co-enrolment) where feasible; blinded central telephone (or postal) assessment of outcomes; and analysis by intention-to-enrol (i.e. all participants) and in pre-specified subgroups.

**32 Publications, published and planned**

1. Protocol: On trial website
2. SAP and baseline data: On trial website
3. Primary results paper: To be published.

**33 Data sharing**

Data will be shared with the VISTA Collaboration.

**Main paper tables****Table 1. Baseline characteristics by treatment group transdermal glyceryl trinitrate (GTN).**

Data are number (%), median [interquartile range] or mean (standard deviation).

† Minimisation variables include age, severity, time, systolic blood pressure, and candidate for or received reperfusion therapy.

Characteristic	Statistic	N	All	GTN	Control
Patients randomised	N		xxx	xxx	xxx
Age (years) †	Mean (SD) (range)	xxx	xxx (xxx) (xxx)	xxx (xxx) (xxx)	xxx (xxx) (xxx)
Sex (males)	n (%)	xxx	xxx (xxx)	xxx (xxx)	xxx (xxx)
Onset to randomisation (minutes) †	Median [IQR] (range)	xxx	xxx [xxx] (xxx)	xxx [xxx] (xxx)	xxx [xxx] (xxx)
Weight	Mean (SD) (range)	xxx	xxx (xxx) (xxx)	xxx (xxx) (xxx)	xxx (xxx) (xxx)
Ethnicity					
...White	n (%)	xxx	xxx (xxx)	xxx (xxx)	xxx (xxx)
...Black	n (%)	xxx	xxx (xxx)	xxx (xxx)	xxx (xxx)
...Asian	n (%)	xxx	xxx (xxx)	xxx (xxx)	xxx (xxx)
...Other	n (%)	xxx	xxx (xxx)	xxx (xxx)	xxx (xxx)
Wake-up stroke	n (%)	xxx	xxx (xxx)	xxx (xxx)	xxx (xxx)
From Nursing home	n (%)	xxx	xxx (xxx)	xxx (xxx)	xxx (xxx)
Medical history					
Diabetes mellitus	n (%)	xxx	xxx (xxx)	xxx (xxx)	xxx (xxx)
Atrial fibrillation	n (%)	xxx	xxx (xxx)	xxx (xxx)	xxx (xxx)
Previous stroke	n (%)	xxx	xxx (xxx)	xxx (xxx)	xxx (xxx)
Previous TIA	n (%)	xxx	xxx (xxx)	xxx (xxx)	xxx (xxx)
IHD	n (%)	xxx	xxx (xxx)	xxx (xxx)	xxx (xxx)
Hyperlipidaemia	n (%)	xxx	xxx (xxx)	xxx (xxx)	xxx (xxx)
PAD	n (%)	xxx	xxx (xxx)	xxx (xxx)	xxx (xxx)
Family stroke	n (%)	xxx	xxx (xxx)	xxx (xxx)	xxx (xxx)
Smoking (%)					
...Current	n (%)	xxx	xxx (xxx)	xxx (xxx)	xxx (xxx)

Characteristic	Statistic	N	All	GTN	Control
...Past	n (%)	xxx	xxx (xxx)	xxx (xxx)	xxx (xxx)
...Never	n (%)	xxx	xxx (xxx)	xxx (xxx)	xxx (xxx)
Alcohol intake (%)					
...High (over 21 units per week)	n (%)	xxx	xxx (xxx)	xxx (xxx)	xxx (xxx)
...Moderate (1-21 units per week)	n (%)	xxx	xxx (xxx)	xxx (xxx)	xxx (xxx)
...None	n (%)	xxx	xxx (xxx)	xxx (xxx)	xxx (xxx)
Existing medications prior to stroke n (%)					
Nitrate therapy	n (%)	xxx	xxx (xxx)	xxx (xxx)	xxx (xxx)
Lipid lowering	n (%)	xxx	xxx (xxx)	xxx (xxx)	xxx (xxx)
Antihypertensives					
Antihypertensives	n (%)	xxx	xxx (xxx)	xxx (xxx)	xxx (xxx)
Diuretic	n (%)	xxx	xxx (xxx)	xxx (xxx)	xxx (xxx)
Beta Blocker	n (%)	xxx	xxx (xxx)	xxx (xxx)	xxx (xxx)
Alpha-blocker	n (%)	xxx	xxx (xxx)	xxx (xxx)	xxx (xxx)
Calcium channel blocker	n (%)	xxx	xxx (xxx)	xxx (xxx)	xxx (xxx)
Angiotensin converting	n (%)	xxx	xxx (xxx)	xxx (xxx)	xxx (xxx)
Angiotensin-II receptor antagonist	n (%)	xxx	xxx (xxx)	xxx (xxx)	xxx (xxx)
Renin	n (%)	xxx	xxx (xxx)	xxx (xxx)	xxx (xxx)
Centrally acting	n (%)	xxx	xxx (xxx)	xxx (xxx)	xxx (xxx)
Labetalol	n (%)	xxx	xxx (xxx)	xxx (xxx)	xxx (xxx)
Other antihypertensives	n (%)	xxx	xxx (xxx)	xxx (xxx)	xxx (xxx)
Antiplatelets					
Aspirin	n (%)	xxx	xxx (xxx)	xxx (xxx)	xxx (xxx)
Dipyridamole	n (%)	xxx	xxx (xxx)	xxx (xxx)	xxx (xxx)
Clopidogrel	n (%)	xxx	xxx (xxx)	xxx (xxx)	xxx (xxx)
Cilostazol	n (%)	xxx	xxx (xxx)	xxx (xxx)	xxx (xxx)
Prasugrel	n (%)	xxx	xxx (xxx)	xxx (xxx)	xxx (xxx)

Characteristic	Statistic	N	All	GTN	Control
Ticagrelor	n (%)	xxx	xxx (xxx)	xxx (xxx)	xxx (xxx)
Anticoagulants					
...Warfarin	n (%)	xxx	xxx (xxx)	xxx (xxx)	xxx (xxx)
...DOACs	n (%)	xxx	xxx (xxx)	xxx (xxx)	xxx (xxx)
...None	n (%)	xxx	xxx (xxx)	xxx (xxx)	xxx (xxx)
Anticoagulants reversal drugs					
None	n (%)	xxx	xxx (xxx)	xxx (xxx)	xxx (xxx)
Vitamin K	n (%)	xxx	xxx (xxx)	xxx (xxx)	xxx (xxx)
Idarucizumab	n (%)	xxx	xxx (xxx)	xxx (xxx)	xxx (xxx)
Prothrombin	n (%)	xxx	xxx (xxx)	xxx (xxx)	xxx (xxx)
FF Plasma	n (%)	xxx	xxx (xxx)	xxx (xxx)	xxx (xxx)
Admission					
Systolic blood pressure (mmHg) †	Mean (SD) (range)	xxx	xxx (xxx) (xxx)	xxx (xxx) (xxx)	xxx (xxx) (xxx)
Diastolic blood pressure (mmHg)	Mean (SD) (range)	xxx	xxx (xxx) (xxx)	xxx (xxx) (xxx)	xxx (xxx) (xxx)
Heart rate (bpm)	Mean (SD) (range)	xxx	xxx (xxx) (xxx)	xxx (xxx) (xxx)	xxx (xxx) (xxx)
Received alteplase†	Yes (%)	xxx	xxx (xxx)	xxx (xxx)	xxx (xxx)
Received mechanical thrombectomy	Yes (%)	xxx	xxx (xxx)	xxx (xxx)	xxx (xxx)
Glasgow coma scale, GCS (/)	Mean (SD) (range)	xxx	xxx (xxx) (xxx)	xxx (xxx) (xxx)	xxx (xxx) (xxx)
DSRS [/12]	Median [IQR] (range)	xxx	xxx (xxx)	xxx (xxx)	xxx (xxx)
NIHSS	Mean (SD) (range)	xxx	xxx (xxx) (xxx)	xxx (xxx) (xxx)	xxx (xxx) (xxx)
Modified Rankin Scale, mRS (pre-stroke)	Median [IQR] (range)	xxx	xxx [xxx] (xxx)	xxx [xxx] (xxx)	xxx [xxx] (xxx)
mRS scores					
...0	n (%)	xxx	xxx (xxx)	xxx (xxx)	xxx (xxx)
...1	n (%)	xxx	xxx (xxx)	xxx (xxx)	xxx (xxx)
...2	n (%)	xxx	xxx (xxx)	xxx (xxx)	xxx (xxx)
...3	n (%)	xxx	xxx (xxx)	xxx (xxx)	xxx (xxx)

Characteristic	Statistic	N	All	GTN	Control
...4 (protocol deviation)	n (%)	xxx	xxx (xxx)	xxx (xxx)	xxx (xxx)
...5	n (%)	xxx	xxx (xxx)	xxx (xxx)	xxx (xxx)
Clinical findings					
Facial weakness	n (%)	xxx	xxx (xxx)	xxx (xxx)	xxx (xxx)
Arm weakness	n (%)	xxx	xxx (xxx)	xxx (xxx)	xxx (xxx)
Leg weakness	n (%)	xxx	xxx (xxx)	xxx (xxx)	xxx (xxx)
Hand side weakness					
...left	n (%)	xxx	xxx (xxx)	xxx (xxx)	xxx (xxx)
...right	n (%)	xxx	xxx (xxx)	xxx (xxx)	xxx (xxx)
...both	n (%)	xxx	xxx (xxx)	xxx (xxx)	xxx (xxx)
... cannot access	n (%)	xxx	xxx (xxx)	xxx (xxx)	xxx (xxx)
Hands: Motor power on affected side					
... normal strength	n (%)	xxx	xxx (xxx)	xxx (xxx)	xxx (xxx)
... reduced strength	n (%)	xxx	xxx (xxx)	xxx (xxx)	xxx (xxx)
... some movement, fingertips do not reach palm	n (%)	xxx	xxx (xxx)	xxx (xxx)	xxx (xxx)
...paralysis	n (%)	xxx	xxx (xxx)	xxx (xxx)	xxx (xxx)
Homonymous hemianopia/ quadrantopia	n (%)	xxx	xxx (xxx)	xxx (xxx)	xxx (xxx)
Neglect	n (%)	xxx	xxx (xxx)	xxx (xxx)	xxx (xxx)
Brainstems signs	n (%)	xxx	xxx (xxx)	xxx (xxx)	xxx (xxx)

Characteristic	Statistic	N	All	GTN	Control
Nutrition					
Feeding ability					
...Normal diet	n (%)	xxx	xxx (xxx)	xxx (xxx)	xxx (xxx)
...Soft diet	n (%)	xxx	xxx (xxx)	xxx (xxx)	xxx (xxx)
...NG feed	n (%)	xxx	xxx (xxx)	xxx (xxx)	xxx (xxx)
...PEG feed	n (%)	xxx	xxx (xxx)	xxx (xxx)	xxx (xxx)
...IV/SC fluids	n (%)	xxx	xxx (xxx)	xxx (xxx)	xxx (xxx)
...Nothing					
Baseline scan information					
Type of scan					
...CT	n (%)	xxx	xxx (xxx)	xxx (xxx)	xxx (xxx)
...MRI	n (%)	xxx	xxx (xxx)	xxx (xxx)	xxx (xxx)
...No scan	n (%)	xxx	xxx (xxx)	xxx (xxx)	xxx (xxx)
Onset to scan (minutes)	Mean (SD) (range)	xxx	xxx (xxx) (xxx)	xxx (xxx) (xxx)	xxx (xxx) (xxx)
Baseline Scan result					
...Normal	n (%)	xxx	xxx (xxx)	xxx (xxx)	xxx (xxx)
...IS no HT	n (%)	xxx	xxx (xxx)	xxx (xxx)	xxx (xxx)
...IS with HT	n (%)	xxx	xxx (xxx)	xxx (xxx)	xxx (xxx)
...PICH	n (%)	xxx	xxx (xxx)	xxx (xxx)	xxx (xxx)
...Other	n (%)	xxx	xxx (xxx)	xxx (xxx)	xxx (xxx)
Presence of compatible lesion	n (%)	xxx	xxx (xxx)	xxx (xxx)	xxx (xxx)
Mass effect	n (%)	xxx	xxx (xxx)	xxx (xxx)	xxx (xxx)
Cerebral atrophy	n (%)	xxx	xxx (xxx)	xxx (xxx)	xxx (xxx)
Periventricular white matter lucency	n (%)	xxx	xxx (xxx)	xxx (xxx)	xxx (xxx)
Hyperdense artery	n (%)	xxx	xxx (xxx)	xxx (xxx)	xxx (xxx)
Previous strokes	n (%)	xxx	xxx (xxx)	xxx (xxx)	xxx (xxx)
CT angiography (CTA)	n (%)	xxx	xxx (xxx)	xxx (xxx)	xxx (xxx)

Characteristic	Statistic	N	All	GTN	Control
...CTA show large vessel occlusion (LVO)	n (%)	xxx	xxx (xxx)	xxx (xxx)	xxx (xxx)
Hospital Utilisations Day 0 and 1					
Received any antihypertensives other than trial patch 1	n (%)	xxx	xxx (xxx)	xxx (xxx)	xxx (xxx)
Received any antihypertensives other than trial patch 2	n (%)	xxx	xxx (xxx)	xxx (xxx)	xxx (xxx)
Treatments given					
Aspirin	n (%)	xxx	xxx (xxx)	xxx (xxx)	xxx (xxx)
Clopidogrel	n (%)	xxx	xxx (xxx)	xxx (xxx)	xxx (xxx)
Dipyridamole	n (%)	xxx	xxx (xxx)	xxx (xxx)	xxx (xxx)
Ticagrelor	n (%)	xxx	xxx (xxx)	xxx (xxx)	xxx (xxx)
Diuretics	n (%)	xxx	xxx (xxx)	xxx (xxx)	xxx (xxx)
Beta-blocker	n (%)	xxx	xxx (xxx)	xxx (xxx)	xxx (xxx)
Alpha-blocker	n (%)	xxx	xxx (xxx)	xxx (xxx)	xxx (xxx)
Calcium channel blocker	n (%)	xxx	xxx (xxx)	xxx (xxx)	xxx (xxx)
Angiotensin-converting enzyme inhibitor	n (%)	xxx	xxx (xxx)	xxx (xxx)	xxx (xxx)
Angiotensin-II receptor antagonist	n (%)	xxx	xxx (xxx)	xxx (xxx)	xxx (xxx)
Renin inhibitors	n (%)	xxx	xxx (xxx)	xxx (xxx)	xxx (xxx)
Centrally acting agent	n (%)	xxx	xxx (xxx)	xxx (xxx)	xxx (xxx)
Labetalol	n (%)	xxx	xxx (xxx)	xxx (xxx)	xxx (xxx)
Other antihypertensive agent	n (%)	xxx	xxx (xxx)	xxx (xxx)	xxx (xxx)
Hemicraniectomy	n (%)	xxx	xxx (xxx)	xxx (xxx)	xxx (xxx)
Mannitol	n (%)	xxx	xxx (xxx)	xxx (xxx)	xxx (xxx)
Intensive care unit admission	n (%)	xxx	xxx (xxx)	xxx (xxx)	xxx (xxx)
Other neurosurgery	n (%)	xxx	xxx (xxx)	xxx (xxx)	xxx (xxx)
Blood pressure lowering used in addition to the trial patch					

Characteristic	Statistic	N	All	GTN	Control
Number of blood lowering drugs used	Median (IQR) (range)	xxx	xxx (xxx) (xxx)	xxx (xxx) (xxx)	xxx (xxx) (xxx)
Intravenous BP lowering drugs used	n (%)	xxx	xxx (xxx)	xxx (xxx)	xxx (xxx)
Combined Alpha- and Beta- blocker	n (%)	xxx	xxx (xxx)	xxx (xxx)	xxx (xxx)
Calcium channel blocker	n (%)	xxx	xxx (xxx)	xxx (xxx)	xxx (xxx)
Glyceryl trinitrate	n (%)	xxx	xxx (xxx)	xxx (xxx)	xxx (xxx)
Diuretic	n (%)	xxx	xxx (xxx)	xxx (xxx)	xxx (xxx)
Sodium nitroprusside	n (%)	xxx	xxx (xxx)	xxx (xxx)	xxx (xxx)
Hydralazine	n (%)	xxx	xxx (xxx)	xxx (xxx)	xxx (xxx)
Transdermal glyceryl trinitrate	n (%)	xxx	xxx (xxx)	xxx (xxx)	xxx (xxx)
Other BP lowering drugs	n (%)	xxx	xxx (xxx)	xxx (xxx)	xxx (xxx)
Main/first reason for blood pressure lowering					
...Preparation for thrombolysis	n (%)	xxx	xxx (xxx)	xxx (xxx)	xxx (xxx)
...Preparation for thrombectomy	n (%)	xxx	xxx (xxx)	xxx (xxx)	xxx (xxx)
...restart pre-stroke antihypertensives	n (%)	xxx	xxx (xxx)	xxx (xxx)	xxx (xxx)
...cerebral oedema	n (%)	xxx	xxx (xxx)	xxx (xxx)	xxx (xxx)
...intracerebral haemorrhage	n (%)	xxx	xxx (xxx)	xxx (xxx)	xxx (xxx)
...stroke mimic	n (%)	xxx	xxx (xxx)	xxx (xxx)	xxx (xxx)
...other reasons	n (%)	xxx	xxx (xxx)	xxx (xxx)	xxx (xxx)

**Table 2. Feasibility measures.**

Data are number (%).

Recruitment of 100 IS patients, 20. We will assess the feasibility of recruiting, treating, and following up patients from 2 centres over three years. We will estimate a recruitment rate, treatment rate and follow-up rate. It is likely that a large definitive trial would be feasible if at least 70 participants were recruited into this study, that compliance with randomised treatment was high and that a high proportion of follow up data was available.

Measure	Metric	N	Achieved
Recruitment			
Overall			xxx/120 (xxx)
Target patients	100 with IS patients		xxx/100 (xxx)
	20 with ICH		xxx/20(xxx)
Primary			
Retention of enrollees at Day 90 (follow-up)	>70 participants	xxx	xxx /100 (xxx)
Treatment compliance/ adherence			
Received GTN	All 2 days treatment	xxx	xxx (xxx)
	First day treatment	xxx	xxx (xxx)
Co-enrolment			
MAPS-2	n(%)		xxx (xxx)
PhEAST	n(%)		xxx (xxx)
ReCAST-3	n(%)		xxx (xxx)
TICH-3	n(%)		xxx (xxx)
MACE-ICH	n(%)		xxx (xxx)
TRIDENT	n(%)		xxx (xxx)
ABC-ICH	n(%)		xxx (xxx)
ENRICH-AF	n(%)		xxx (xxx)
ATTEST-I	n(%)		xxx (xxx)
TASTE	n(%)		xxx (xxx)
OPTIMAS	n(%)		xxx (xxx)
ProFATE	n(%)		xxx (xxx)
Mrna-1273-P305	n(%)		xxx (xxx)
COMMITTS	n(%)		xxx (xxx)
OPTIMIST	n(%)		xxx (xxx)

**Table 3. Clinical Outcomes at Day 90.**

Data are number (%), median [interquartile range] or mean (standard deviation). Analyses performed using binary logistic regression (BLR), ordinal logistic regression (OLR) or multiple linear regression (MLR) with adjustment for age, time from stroke onset to randomisation, systolic blood pressure, stroke severity (NIHSS), and received reperfusion therapy. Mean (SD) and MLR will be used instead of median [IQR] and OLR for ordinal scales with more than 7 levels (central limit theorem/large sample). Cox proportional hazards regression (CPHR) will be used for death.

Variable	Statistic	N	All	GTN	Sham	aOR/aHR/aMD (95%CI)	Difference (p)
Patients randomised	N	xxx	xxx	xxx	xxx		
Outcomes							
Functional, modified Rankin scale (/6)							
	Median [IQR]	xxx	xxx [xxx]	xxx [xxx]	xxx [xxx]	xxx (xxx, xxx)	aOLR
	Mean (SD)	xxx	xxx [xxx]	xxx [xxx]	xxx [xxx]	xxx (xxx, xxx)	OLR aMLR
0	n(%)	xxx	xxx (xxx)	xxx (xxx)	xxx (xxx)		
1	n (%)	xxx	xxx (xxx)	xxx (xxx)	xxx (xxx)		
2	n (%)	xxx	xxx (xxx)	xxx (xxx)	xxx (xxx)		
3	n (%)	xxx	xxx (xxx)	xxx (xxx)	xxx (xxx)		
4	n (%)	xxx	xxx (xxx)	xxx (xxx)	xxx (xxx)		
5	n (%)	xxx	xxx (xxx)	xxx (xxx)	xxx (xxx)		
6	n (%)	xxx	xxx (xxx)	xxx (xxx)	xxx (xxx)		
Death	n (%)	xxx	xxx (xxx)	xxx (xxx)	xxx (xxx)	xxx (xxx, xxx)	CPHR
Disability							
Barthel index, BI (/100)	Mean (SD)	xxx	xxx (xxx)	xxx (xxx)	xxx (xxx)	xxx (xxx, xxx)	MLR
Cognition							
Telephone, MMSE (/22)	Mean (SD)	xxx	xxx (xxx)	xxx (xxx)	xxx (xxx)	xxx (xxx, xxx)	MLR
TICS-M (/39)	Mean (SD)	xxx	xxx (xxx)	xxx (xxx)	xxx (xxx)	xxx (xxx, xxx)	MLR
Animal naming	Mean (SD)	xxx	xxx (xxx)	xxx (xxx)	xxx (xxx)	xxx (xxx, xxx)	MLR
Mood							
Zung depression scale, ZDS(/102.5)	Mean (SD)	xxx	xxx (xxx)	xxx (xxx)	xxx (xxx)	xxx (xxx, xxx)	MLR

Variable	Statistic	N	All	GTN	Sham	aOR/aHR/aMD (95%CI)	Difference (p)
Quality of Life							
EQ-5D HSUV (/1)	Mean (SD)	xxx	xxx (xxx)	xxx (xxx)	xxx (xxx)	xxx (xxx, xxx)	OLR
EQ-VAS (/100)	Mean (SD)	xxx	xxx (xxx)	xxx (xxx)	xxx (xxx)	xxx (xxx, xxx)	OLR
Disposition						xxx (xxx, xxx)	OLR
...Home	n (%)	xxx	xxx (xxx)	xxx (xxx)	xxx (xxx)		
...Institution/in hospital	n (%)	xxx	xxx (xxx)	xxx (xxx)	xxx (xxx)		
...Died	n (%)	xxx	xxx (xxx)	xxx (xxx)	xxx (xxx)		
Events							
Recurrent Stroke	n (%)	xxx	xxx (xxx)	xxx (xxx)	xxx (xxx)	xxx (xxx, xxx)	BLR
Acute Coronary Syndrome	n (%)	xxx	xxx (xxx)	xxx (xxx)	xxx (xxx)	xxx (xxx, xxx)	BLR
Elective rehabilitation admission	n (%)	xxx	xxx (xxx)	xxx (xxx)	xxx (xxx)	xxx (xxx, xxx)	BLR
Viral Infections	n (%)	xxx	xxx (xxx)	xxx (xxx)	xxx (xxx)	xxx (xxx, xxx)	BLR

BI: Barthel Index, TICS-m: Telephone interview cognitive scale- modified; t-MMSE: telephone Mini-Mental State Examination ; ZDS: Zung depression scale; quality of life (EQ-5D HSUV, EQ-VAS).

Death scores: mRS (6); BI (5); TICS-m (-1); ZDS (102.5); EQ-5D HSUV (0); EQ-VAS (-1)

**Table 4. Clinical Outcomes at Day 2.**

Data are number (%), median [IQR], or mean (standard deviation).

Variable	Statistic	N	All	GTN	Sham	aOR/aMD (95%CI)	Difference (p)
Patients randomised	N	xxx	xxx	xxx	xxx		
Mechanistic Outcomes							
Blood Pressure							
SBP (mmHg)	Mean (SD)	xxx	xxx (xxx)	xxx (xxx)	xxx (xxx)	xxx (xxx, xxx)	MLR
DBP (mmHg)	Mean (SD)	xxx	xxx (xxx)	xxx (xxx)	xxx (xxx)	xxx (xxx, xxx)	MLR
Heart rate (bpm)	Mean (SD)	xxx	xxx (xxx)	xxx (xxx)	xxx (xxx)	xxx (xxx, xxx)	MLR
Clinical Outcomes							
Impairment							
NIHSS (/100)	Mean (SD)	xxx	xxx (xxx)	xxx (xxx)	xxx (xxx)	xxx (xxx, xxx)	MLR
Neurological deterioration NIHSS change from baseline (point increase)							
NIHSS ≥ 4	Mean (SD)	xxx	xxx (xxx)	xxx (xxx)	xxx (xxx)	xxx (xxx, xxx)	MLR
NIHSS ≥ 2	Mean (SD)	xxx	xxx (xxx)	xxx (xxx)	xxx (xxx)	xxx (xxx, xxx)	MLR
Hand weakness						xxx (xxx, xxx)	OLR
...Normal strength	n (%)	xxx	xxx (xxx)	xxx (xxx)	xxx (xxx)		
...Reduced strength	n (%)	xxx	xxx (xxx)	xxx (xxx)	xxx (xxx)		
...Some movement	n (%)	xxx	xxx (xxx)	xxx (xxx)	xxx (xxx)		
...Paralysis	n (%)	xxx	xxx (xxx)	xxx (xxx)	xxx (xxx)		
Feeding ability						xxx (xxx, xxx)	OLR
...Normal diet	n (%)	xxx	xxx (xxx)	xxx (xxx)	xxx (xxx)		
...Soft diet	n (%)	xxx	xxx (xxx)	xxx (xxx)	xxx (xxx)		
...NG feed	n (%)	xxx	xxx (xxx)	xxx (xxx)	xxx (xxx)		
...PEG feed	n (%)	xxx	xxx (xxx)	xxx (xxx)	xxx (xxx)		
...IV/SC fluids	n (%)	xxx	xxx (xxx)	xxx (xxx)	xxx (xxx)		
...Nothing	n (%)	xxx	xxx (xxx)	xxx (xxx)	xxx (xxx)		
Dysphagia, DSRS (/12)	Mean (SD)	xxx	xxx (xxx)	xxx (xxx)	xxx (xxx)	xxx (xxx, xxx)	MLR
Events up to day 2							
Death	n (%)	xxx	xxx (xxx)	xxx (xxx)	xxx (xxx)	xxx (xxx, xxx)	BLR
Symptomatic ICH	n (%)	xxx	xxx (xxx)	xxx (xxx)	xxx (xxx)	xxx (xxx, xxx)	BLR
ICH expansion	n (%)	xxx	xxx (xxx)	xxx (xxx)	xxx (xxx)	xxx (xxx, xxx)	BLR
Symptomatic Recurrent Stroke						xxx (xxx, xxx)	OLR

Variable	Statistic	N	All	GTN	Sham	aOR/aMD (95%CI)	Difference (p)
...IS	n (%)	xxx	xxx (xxx)	xxx (xxx)	xxx (xxx)		
...haemorrhagic	n (%)	xxx	xxx (xxx)	xxx (xxx)	xxx (xxx)		
...unknown type	n (%)	xxx	xxx (xxx)	xxx (xxx)	xxx (xxx)		
...none	n (%)	xxx	xxx (xxx)	xxx (xxx)	xxx (xxx)		
Clinical neuro-deterioration	n (%)	xxx	xxx (xxx)	xxx (xxx)	xxx (xxx)	xxx (xxx, xxx)	BLR
MEB	n (%)	xxx	xxx (xxx)	xxx (xxx)	xxx (xxx)	xxx (xxx, xxx)	BLR
Acute coronary Syndrome (ACS)	n (%)	xxx	xxx (xxx)	xxx (xxx)	xxx (xxx)	xxx (xxx, xxx)	BLR
...STEMI							
...NSTEMI							
...Unstable angina							
...None							
Symptomatic pulmonary embolism	n (%)	xxx	xxx (xxx)	xxx (xxx)	xxx (xxx)	xxx (xxx, xxx)	BLR
Headache	n (%)	xxx	xxx (xxx)	xxx (xxx)	xxx (xxx)	xxx (xxx, xxx)	BLR
Hypotension	n (%)	xxx	xxx (xxx)	xxx (xxx)	xxx (xxx)	xxx (xxx, xxx)	BLR
Hypertension	n (%)	xxx	xxx (xxx)	xxx (xxx)	xxx (xxx)	xxx (xxx, xxx)	BLR

Please note:

ACS (Acute coronary syndrome); DPB (diastolic blood pressure); DSRS (dysphagia rating scale); IV (intravenous); MEB (major extracranial bleeding); NIHSS (NIH Stroke Scale); NG (nasogastric); NSTEMI; PE (Pulmonary embolism); PEG (percutaneous endoscopic gastrostomy); SC (subcutaneous); SPB (systolic blood pressure); STEMI.

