**14 Table C.-Timing of outcome assessments**

Assessments	Screen	Day 0 Baseline Pre- treatment	Day 0 Post- treatment	Day 1 During treatment	Day 2 After treatment	Discharge, Death	Day 90 Telephone
Face-to-face							
Clinical assessment	X 				X	X	
Eligibility screening	X						
CT Scan		X 	or X 				
Consent		X		or X	or X		
Randomisation		X					
GTN/Sham patch			X	X			
mRS		X 					
U & E FBC		X 					
Blood pressure		X 	X	X			
NIHSS		X 			X		
DSRS		X			X		
Blood biomarkers		X 			X 		

Hospital utilisation						X 	
Listed events				X 	X 		
SAEs, non-fatal			X	X	X		
SAEs fatal				X	X	X	X 
mRS							X 
Barthel Index							X 
EuroQoL							X 
Cognition (t-MMSE, TICS)							X 
Mood (ZDS)							X 

CT: Computerised tomography

NIHSS: National Institutes of Health stroke scale

MMSE: Mini-Mental State Examination

mRS modified Rankin scale

SAEs: Serious Adverse Events

1. Routine as part of clinical practice

2. Pre-morbid mRS

3. Biomarkers: soluble markers, genetics

4. Open-label blood pressure lowering, intravenous thrombolysis, mechanical thrombectomy, hyperacute stroke unit, Stroke Rehabilitation Unit, physiotherapy, occupational therapy, speech & language therapy, surgery for IS – hemicraniectomy, surgery for ICH, days in intensive/critical care unit.

5. Hypotension, hypertension, headache, infection

6. mRS [0 to 5, death=6], NIHSS [0 to 42, death=43], DSRS [0 to 12, death=13], GCS [3 to 15, death=2], BI [0 to 100, death=-5], EQ-5D [-0.5 to 1.0, death=0], EQ-VAS [0 to 100, death=-1], t-MMSE [0 to 22, death=-1], TICS-m [0 to 39, death=-1] and ZDS [ $\geq 70$ , death=102.5].

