#### ***24b Secondary endpoints***

1. Hospital admission:
  - Neurological impairment (NIHSS)
  - Systolic and diastolic blood pressure, heart rate.
  - Proportion of participants with systolic blood pressure <185 mmHg.
  - Feeding and dysphagia (dysphagia severity rating scale)
  - Stroke lesion size on brain scan (non-contrast CT or T2 MR).
  - Amount of cerebral arterial patency on brain scan (CT or MR angiography).
2. Hospital utilisation:
  - Open-label blood pressure lowering.
  - Intravenous thrombolysis.
  - Mechanical thrombectomy.
  - Hyperacute stroke unit.
  - Stroke Rehabilitation Unit.
  - Physiotherapy.
  - Occupational therapy.
  - Speech & language therapy.
  - Surgery for IS - Hemicraniectomy.
  - Surgery for ICH.
  - Days in intensive/critical care unit.
3. At day 2:
  - Systolic and diastolic blood pressure, heart rate.

4. At day 2: Biomarkers
  - Blood biomarkers (exact measures to be determined by literature review prior to measurement but examples include S-100, NOx).
  - Genetic markers (exact measures to be determined by literature review prior to measurement but examples include NO synthase polymorphisms).
5. At day 2 (or discharge if sooner):
  - Neurological impairment (NIHSS).
  - Stroke recurrence.
  - Neurological deterioration from baseline (NIHSS  $\geq 4$  points, or  $\geq 2$ -point increase in any domain).
  - Feeding and dysphagia (DSRS).
6. At discharge/death
  - Length of stay in hospital.
  - Patient disposition.
7. At day 90 by telephone (or post):
  - Dependency – modified Rankin Scale (primary clinical endpoint at Day 90).
  - Disability/activities of daily living - Barthel Index (BI).
  - Quality of life - health utility status (HUS, derived from EuroQoL-5D), EQ-Visual Analogue Scale (EQ-VAS).
  - Cognition - telephone-MMSE, telephone interview cognition scale (TICS), animal naming.
  - Mood - Zung depression scale.
  - Patient disposition (died, institution/in hospital, home).

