**Table D. Descriptive and analytical statistics**

	Nominal	Binary	Ordinal	Continuous	Time to Event
Central tendency	N (%)	N (%)	Median [interquartile	Mean (standard	N (%)

and distribution			range]	deviation)	
Comparisons	Chi-square (2x2, or rxc)	Chi-square (2x2)	Mann-Whitney U	t-test (pooled) change from baseline-Repeat Measures (RM)	
Regression	-	Binary logistic regression (BLR)	Ordinal logistic regression (OLR)	Multiple linear regression (MLR)	Cox proportional hazards regression (CPHR)

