**Table 6. Outcomes at Discharge.**

Data are number (%) and mean (standard deviation).

Variable	Statistic	N	All	GTN	Control	aOR/aMD (95%CI)	Difference (p)
Patients randomised	N	xxx	xxx	xxx	xxx		
Disposition Outcomes							
Discharge destination						xxx (xxx, xxx)	OLR
...Home	n (%)	xxx	xxx (xxx)	xxx (xxx)	xxx (xxx)		
...Institution	n (%)	xxx	xxx (xxx)	xxx (xxx)	xxx (xxx)		
...Hospital	n (%)	xxx	xxx (xxx)	xxx (xxx)	xxx (xxx)		
...Died	n (%)	xxx	xxx (xxx)	xxx (xxx)	xxx (xxx)		
...Other	n (%)	xxx	xxx (xxx)	xxx (xxx)	xxx (xxx)		
Length of stay in hospital, days	Mean (SD)	xxx	xxx (xxx)	xxx (xxx)	xxx (xxx)	xxx (xxx, xxx)	MLR
Hospital Interventions							
Acute stroke unit, ASU	n (%)	xxx	xxx (xxx)	xxx (xxx)	xxx (xxx)	xxx (xxx, xxx)	BLR
Length of stay in ASU, days	Mean (SD)	xxx	xxx (xxx)	xxx (xxx)	xxx (xxx)	xxx (xxx, xxx)	MLR
Intensive therapy/high dependency unit (ITU/HDU)	n (%)	xxx	xxx (xxx)	xxx (xxx)	xxx (xxx)	xxx (xxx, xxx)	BLR
Length of stay in ITU/HDU, days	Mean (SD)	xxx	xxx (xxx)	xxx (xxx)	xxx (xxx)	xxx (xxx, xxx)	MLR
Stroke rehabilitation unit (SRU)	n (%)	xxx	xxx (xxx)	xxx (xxx)	xxx (xxx)	xxx (xxx, xxx)	BLR
Length of stay in SRU, days	Mean (SD)	xxx	xxx (xxx)	xxx (xxx)	xxx (xxx)	xxx (xxx, xxx)	MLR
Non-stroke ward	n (%)	xxx	xxx (xxx)	xxx (xxx)	xxx (xxx)	xxx (xxx, xxx)	BLR
Length of stay in non-stroke ward	Mean (SD)	xxx	xxx (xxx)	xxx (xxx)	xxx (xxx)	xxx (xxx, xxx)	MLR
Physiotherapy	n (%)	xxx	xxx (xxx)	xxx (xxx)	xxx (xxx)	xxx (xxx, xxx)	BLR
Occupational therapy	n (%)	xxx	xxx (xxx)	xxx (xxx)	xxx (xxx)	xxx (xxx, xxx)	BLR
Speech and language therapy	n (%)	xxx	xxx (xxx)	xxx (xxx)	xxx (xxx)	xxx (xxx, xxx)	BLR
Dietician	n (%)	xxx	xxx (xxx)	xxx (xxx)	xxx (xxx)	xxx (xxx, xxx)	BLR
Intermittent pneumatic compression stockings	n (%)	xxx	xxx (xxx)	xxx (xxx)	xxx (xxx)	xxx (xxx, xxx)	BLR
Results of carotid ultrasound (stenosis)							

Variable	Statistic	N	All	GTN	Control	aOR/aMD (95%CI)	Difference (p)
Left stenosis	Mean (SD)	xxx	xxx (xxx)	xxx (xxx)	xxx (xxx)	xxx (xxx, xxx)	MLR
Right stenosis	Mean (SD)	xxx	xxx (xxx)	xxx (xxx)	xxx (xxx)	xxx (xxx, xxx)	MLR
Do not resuscitate (DNR)	n (%)	xxx	xxx (xxx)	xxx (xxx)	xxx (xxx)	xxx (xxx, xxx)	BLR
Final Diagnosis of the randomising event							
Stroke diagnosis							OLR
...Ischaemic stroke	n (%)	xxx	xxx (xxx)	xxx (xxx)	xxx (xxx)	xxx (xxx, xxx)	
...PICH	n (%)	xxx	xxx (xxx)	xxx (xxx)	xxx (xxx)	xxx (xxx, xxx)	
...TIA	n (%)	xxx	xxx (xxx)	xxx (xxx)	xxx (xxx)	xxx (xxx, xxx)	

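### Several SAP table shells contradict the SAP's own rules on method and scoring, and would give wrong or arbitrary secondary results if programmed as written

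*SAP*

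**What the plan says.** **Governing rule.** SAP section 25a sends all summaries and regressions to Table D. For a binary variable Table D gives N (%) and "Binary logistic regression (BLR"). For a nominal variable it gives N (%) and "Chi-square (2x2, or rxc"), with a dash in the regression cell.

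**Deterioration.** SAP section 24b lists "Neurological deterioration from baseline" as one day-2 endpoint, met by an NIHSS change of at least 4 points or a rise of at least 2 in any domain. Table 4 shows two rows under "Neurological deterioration NIHSS change from baseline (point increase", namely 'NIHSS ≥ 4' and 'NIHSS ≥ 2', each with mean (SD) and MLR. Further down, the same table has a row 'Clinical neuro-deterioration' with n (%) and BLR.

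**Categories.** OLR is set for symptomatic recurrent stroke in Table 4 (IS, haemorrhagic, unknown type, none). It is also set for stroke diagnosis in Table 6 (ischaemic stroke, PICH, TIA, subarachnoid haemorrhage, unknown) and for "Discharge destination" in Table 6 (home, institution, hospital, died, other).

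**Quality of life.** The Table 3 header states: "Mean (SD) and MLR will be used instead of median [IQR] and OLR for ordinal scales with more than 7 levels". Section 25c names multiple linear regression for EQ-5D and EQ-VAS. The Table 3 rows for both show mean (SD) but OLR.

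**Barthel deaths.** The Table 3 footnote reads "Death scores: mRS (6); BI (5); TICS-m (-1"). Footnote 6 to SAP Table C reads "BI [0 to 100, death=-5"], and protocol Appendix D also assigns -5.

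**The concern.** The shells are the only row-by-row instruction the programmer has. Where a shell and the text disagree, someone must choose after the SAP is signed, which is what pre-specification is meant to prevent. The text does not settle every conflict: section 25c refers the reader to Table A, which lists the earlier GTN trials, when Table D appears to be meant.

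At stake are the interpretability of the deterioration result, common odds ratios whose value depends on an arbitrary listing order, a mean summary paired with an odds-ratio model, and a Barthel comparison in which a death scores better than some survivors.

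**Working it through.** No sample-size, power or alpha figure enters this point, so there is no stated calculation to reproduce. The check compares the shells with the rules, with two illustrations of size.

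| Item | Shell | Rule elsewhere | Conflict |
|---|---|---|---|
| Deterioration | Table 4: two rows, mean (SD), MLR | 24b: one yes/no endpoint; Table D: N (%), BLR | Type, method and definition |
| Recurrent stroke, day 2 | Table 4: OLR on type | Table D: no regression for nominal data; Table 3 at day 90: BLR | Method |
| Final stroke diagnosis | Table 6: OLR | Table D: chi-square, no regression | Method |
| EQ-5D HSUV, EQ-VAS | Table 3: mean (SD), OLR | 25c and Table 3 header: MLR | Method |
| Barthel, death | Table 3 footnote: 5 | Table C and Appendix D: -5 | Score |

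**(a) Deterioration.** The rows can be read as the mean of a 0/1 indicator, or as the mean rise among those who crossed the threshold. The second conditions on a post-randomisation outcome, and neither is what Table D asks for. Dropping the domain condition also changes the endpoint. Read as a total-score rule, the ≥ 2 row counts two 1-point rises in different domains. It misses a 2-point rise in one domain that is offset by gains elsewhere.

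**(b) Order dependence.** Proportional-odds models were fitted to assumed counts, 60 per arm; these are illustrations, not trial data.

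- Recurrent stroke (IS / haemorrhagic / unknown / none): GTN 1/4/1/54, sham 5/1/1/53. The common OR is 1.26 in the listed order and 1.13 with IS and haemorrhagic swapped. The OR for none versus any is (54/6)/(53/7) = 1.19.
- Diagnosis (IS / PICH / TIA / SAH / unknown): GTN 45/8/4/0/3, sham 38/12/7/1/2. The common OR is 0.60 in the listed order, 0.87 in the order TIA, IS, unknown, PICH, SAH, and 1.09 with PICH and IS swapped. The direction itself depends on the order.

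The SAP already has a sound pattern for this layout: acute coronary syndrome in Table 4, with subtypes and a none row, is set to BLR.

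**(c) EQ-5D and EQ-VAS.** EQ-VAS runs from 0 to 100 and the EQ-5D utility from -0.5 to 1.0 (Table C, footnote 6). Both have more than 7 levels, so the Table 3 header selects MLR, in agreement with 25c.

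**(d) Barthel.** Scoring death as 5 instead of -5 raises an arm's mean by 10 × its death proportion. The GTN minus control difference therefore changes by 10 × (p_GTN − p_control). Death percentages and Barthel differences are from SAP Table B:

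| Source | Deaths, GTN v control | Change in difference | Tabulated difference |
|---|---|---|---|
| ENOS | 12% v 13% | 10 × (0.12 − 0.13) = −0.1 | 2.18 |
| RIGHT-2 | 23% v 19% | 10 × (0.23 − 0.19) = +0.4 | −3 |
| ENOS-early | 8% v 20% | 10 × (0.08 − 0.20) = −1.2 | 14 |

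In all three the change is towards zero, because the arm with more deaths also has the lower Barthel score. As shares of the tabulated differences these are 0.1/2.18 = 5%, 0.4/3 = 13% and 1.2/14 = 9%. The percentages are rounded to whole numbers, so each change is uncertain by up to about 10 × 0.01 = 0.1.

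For scale, with the ENOS-early SDs (34 and 41) and 60 scored per arm, the standard error of the difference is √((34² + 41²)/60) = √(2837/60) = 6.9 points.

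**The case against.** The best defence is that none of this touches what the trial is for. The primary endpoint is the feasibility of recruiting and treating 120 patients. The protocol plans no confirmatory efficacy analysis, and section 25c calls these comparisons exploratory. An attentive programmer would follow Table D and the Table 3 header, and the Barthel 5 is probably a lost minus sign. Ordinal regression on EQ-VAS is a legitimate method in itself, and the recurrent-stroke illustration shows only a modest distortion around 1.19. All of this stands as to weight. It does not remove the contradictions. The minus signs for TICS-m and EQ-VAS survive in the same footnote, so a general loss of signs in reading the PDF is unlikely.

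A reader might go further in four ways that the documents do not support.

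- *That deterioration would have no proportion or odds ratio.* The 'Clinical neuro-deterioration' row supplies both. The fault is that the row is undefined and not linked to the 24b definition.
- *That DMC safety monitoring is compromised.* The DMC is to monitor deterioration, but through its own six-monthly reports and unmasked reviews. Table 4 belongs to the main paper tables, and nothing ties the DMC's work to it.
- *That discharge destination is unordered, or that 'Other' is ranked worse than death.* Home, institution, hospital and died can be ordered, and the SAP does not say that the printed row order is the model coding. Only the place of 'Other' is open.
- *That the Barthel error is typically 1.2 points.* That is the largest of the three values; the range is about 0.1 to 1.2.

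**Conclusion.** The shells are wrong as written in four places: the deterioration rows, OLR for recurrent-stroke type and final stroke diagnosis, OLR for EQ-5D and EQ-VAS, and the Barthel death score. Each conflicts with another part of the SAP, and the Barthel score also with the protocol, so no outside source is needed to establish the point. EQ-5D and EQ-VAS are a matter of inconsistency rather than invalid method.

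The Barthel effect is about 0.1 to 1.2 points, assuming death rates like those in Table B and that every death is scored. Even the largest value is small beside a standard error of about 7 points. The order-dependence figures rest on assumed counts and show only that the estimate, and for diagnosis its direction, can depend on the chosen order. The primary endpoint and the mRS analysis are unaffected. The corrections should be made before programming, but the point does not threaten the trial's main conclusion.

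**What to change.** Amend the SAP shells before programming and before treatment codes are released:

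- **Table 4, deterioration:** replace the two threshold rows with one row, an NIHSS increase of at least 4, or at least 2 in any domain, with n (%) and BLR. Define 'Clinical neuro-deterioration' or merge it into that row.
- **Table 4, recurrent stroke:** any versus none by BLR, as at day 90 in Table 3, with types shown as counts.
- **Table 6, final stroke diagnosis:** n (%) with chi-square, or counts only.
- **Table 6, discharge destination:** state the category order, and reclassify or exclude 'Other'.
- **Table 3, EQ-5D HSUV and EQ-VAS:** MLR.
- **Table 3 footnote:** Barthel death score -5, matching Table C and Appendix D.
- **Section 25c:** correct the reference to Table A, apparently meant for Table D.

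The cost is a short SAP revision. Assessments and trial conduct do not change; the domain condition needs NIHSS item scores, which protocol Appendix C already tells assessors to record.
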